	In addition, demonstration of bone consolidation in correct alignment will be measured by Investigator assessment by 12 months.
	Safety of the T2 Alpha Tibia Nailing System will be demonstrated through reporting of device related intra-operative and post-operative Adverse Events/incidents by 12 months.
Target Population	Approximately 80 subjects are to be enrolled in this clinical investigation at up to 5 sites. Enrolled subjects will be assessed at Operative/Discharge, and at 3 Months, 6 Months and 12 Months after the index procedure.
Inclusion	a. Subject is a male or non-pregnant female age 18 years or older at the time of surgery;
Criteria	b. Subject is willing and able to give written informed consent and comply with the requirements of this Clinical Investigation Plan;
	c. Subject is intended to be treated with the Tibial Nail of the T2 Alpha Tibia Nailing System in accordance with the following legally cleared/approved Indications for Use:
	Indications for Use approved In United States and Canada include:
	 Open and closed tibial fractures Pseudoarthrosis and correction osteotomy
	 Pathologic fractures, impending pathologic fractures and tumor resections Fractures involving osteopenic and osteoporotic bone Nonunions and malunions
	Indications for Use approved In Europe and Other Countries include:
	 Open and closed tibial fractures Nonunions and malunions

543

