8.2. SECONDARY ENDPOINTS

- Safety: Incidence of device-related adverse events by 12 months will be monitored through collection and analyses.
- Efficacy/Performance: Bone consolidation will be assessed by 12 months as measured by Investigator assessment.

9. Selection of Clinical Investigation Population

Subjects participating in this clinical investigation will be recruited from the investigator's standard subject population, where all subjects presenting for treatment of tibial fractures will be evaluated for clinical investigation participation based on the eligibility criteria listed below.

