3.1.2. Secondary Analyses

For efficacy/performance, bone consolidation will be assessed by 12 months as measured by Investigator assessment. For Safety, the incidence of device-related adverse events/incidents by 12 months will be monitored through collection and analyses. Both analyses will be part of the final report.

Furthermore, device related adverse events/incidents and the time to (earliest) Device Related Adverse Events/incidents will be analyzed as well. Considered variables, the level of measurement and the planned analysis steps are listed in detail in the SAP.

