4.4. TIMING OF OUTCOME ASSESSMENT

Subjects in this clinical investigation will be evaluated at Operative/Discharge, and at 3 Months, 6 Months and 12 Months after the index procedure. The follow-up evaluations will include assessment of device-related adverse events/incidents, evaluation per SF-36 PCS and MCS scores as well as clinical assessment of bone consolidation. Investigators should consider weight-bearing, pain and imaging when assessing bone consolidation. See the section below for visit windows and a list of assessments to be performed at each visit, given by the CIP.

Assessment	Operative/ Discharge	3 Months ^{a, b} (+/-2 weeks)	6 Months ^{a, b} (+/-3 weeks)	12 Months ^b (+/-4 weeks)		
Informed Consent	Xc					
Demographics & Medical History	Х					
Inclusion/Exclusion	Х					
Primary Diagnosis	Х					
Surgical Procedure	Х					
Clinical Assessment of Bone Consolidation ^{d, e}		Х	Х	Х		
SF-36v2 (PCS & MCS)	X f	Х	X ^g	X ^g		
Subject Disposition ^h		Х	Х	Х		
Device-Related Adverse Events/Incidents & Reoperations will be collected throughout the course of the Clinical Investigation.						

- a. Follow-up visit schedule to reflect Institutions' Standard of Care practices
- b. If the subject missed a visit and outside of visit window, every effort should be made to collect data instead of noting visit as missed. Visit windows are calculated from the index event, and not from the previous visit.
- c. Informed consent must be obtained prior to enrollment in the study (i.e., prior to performance of any study-related activities).
- d. Once bone consolidation is observed, assessment no longer needs to be conducted at the additional follow-up visits.
- e. Investigators should consider weight-bearing, pain and imaging when assessing bone consolidation.
- f. SF-36v2 evaluation must be collected post-informed consent. This can be collected post-fracture and prior to surgery or immediately post-surgery.
- g. If bone consolidation is previously observed at the previous follow-up visit, evaluation is to be collected via phone.
- h. Subject Disposition assessment would occur at any time point for subject withdrawal prior to the completion of the clinical investigation.

 Table 4.4: Assessments and Clinical Investigation Elements

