4.6. MISSING DATA

The intent is to collect as complete a dataset as possible. Nevertheless, in some situations missing data cannot be avoided. The reports and tables therefore will show the number and percentage of missing cases for each analyzed variable in relation to the enrolled cases for each post-operative assessment.

Missing data will be reported for each variable or calculation (if any) and overall totals will be reported including the proportion of missing data (if any).

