6.5. POST-OPERATIVE CHARACTERISTICS

The analysis of the Postoperative data must be performed separately for each follow-up visit listed in table 4.4 in accordance to the following tables in this chapter. New Variables must be created individually for each follow-up visit.

Evaluation	Level of						
Variable / Ouestion	Measurement	Analysis Plan	I	nclusio	n		
Post-Operative Visit Form – Ph	ysical Exam		IR	FR	N/A		
Date of Visit:	Date/Time	None			Х		
Creation of variable Difference between Date of Surgery [dd.mm.yyyy] and Date of Visit [dd.mm.yyyy] In [days] (Variable(s): VISITID; VISNAME)	Case summary with number and percentage of valid cases/values, missing cases/values (if any) and total cases/values.Quantitative, ratioMean, median, interquartile range, maximum, minimum, standard deviation, 95% confidence interval for mean, Shapire Wilk Tast		Quantitative, ratio Quanti			х	
Is the subject weight bearing? (Variable(s): WEIGHTBEAR)	Qualitative, nominal	Proportions, frequencies, column and row totals, missing proportion (if any).	Х	Х			
Specify, Full or Partial (Variable(s): FULPART)	Qualitative, nominal	Proportions, frequencies, column and row totals, missing proportion (if any).	Х	Х			
Is the subject using an external support? (Variable(s): EXTRSUPP)	Qualitative, nominal	Proportions, frequencies, column and row totals, missing proportion (if any).	X	Х			
Has the bone consolidated (consider weight-bearing, pain and imaging)? (Variable(s): BONECONS; EXPLN)	Qualitative, nominal	Proportions, frequencies, column and row totals, missing proportion (if any). Listing of given explanations.	Х	Х			

Table 6.5.1: Post-Operative Visit Form – Physical Exam Tables List

Evaluation	Level of Massurament			clusion	
Post-Onerative Visit Form – SF	-36 Score		IR	FR	N/A
In general, would you say your health is (Variable(s): GH01 RESPONSE)	Qualitative, nominal	Proportions, frequencies, column and row totals, missing proportion (if any).			X
Compared to one year ago, how would you rate your health in general now? (Variable(s): HT RESPONSE)	Qualitative, nominalProportions, frequencies, column and row totals, missing proportion (if any).				х
Vigorous activities, such as running, lifting heavy objects, participating in strenuous sports (Variable(s): PF01_RESPONSE)	Qualitative, nominalProportions, frequencies, column and row totals, missing proportion (if any).				Х

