6.6. ANALYSIS OF CI ENDPOINTS

Evaluation Variable / Question	Level of Measurement	Analysis Plan
Endpoints – Primary Endpoint		

Use variable SF-36 Total Physical Score 12 Months [points]:

Based on the underlying distribution of the data and the result of the normality assessment, either the parametric onesample t-test or the non-parametric one-sample sign test will be used to compare the 12 months post-operative SF-36 score results of the T2 Alpha Tibia group against the value of 39.25 points.

The complete available SPSS tables content related to either the one-sample t-test or the one-sample sign test will be included in the final report (under no circumstances, creation of this analysis in any interim/annual report). (Variable(s): VISITDT; PCSSCORE)

Evaluation Variable / Question	Level of Measurement	Recode and Analysis Plan	Ir	nclusio	n
All Assessments – Fracture Healing		IR	FR	N/A	
3 Months - 4. Has the bone consolidated (consider weight- bearing, pain and imaging)? (Variable(s): VISITDT; BONECONS)	Qualitative, nominal	Proportions, frequencies, column and row totals, missing proportion (if any).		X	
6 Months - 4. Has the bone consolidated (consider weight- bearing, pain and imaging)? (Variable(s): VISITDT; BONECONS)	Qualitative, nominal Proportions, frequencies, column and row totals, missing proportion (if any).			X	
12 Months - 4. Has the bone consolidated (consider weight- bearing, pain and imaging)? (Variable(s): VISITDT; BONECONS)	Qualitative, nominal	Proportions, frequencies, column and row totals, missing proportion (if any).		Х	

Table 6.6.1: Endpoints - Primary Endpoint Tables List

Table 6.6.2: Endpoints - Secondary Endpoint Fracture Healing Tables List

Evaluation Variable / Ouestion	Level of Measurement	Recode and Analysis Plan	Iı	nclusio	on
Adverse Events – Time to (earliest) Device Related Adverse Event / Incident			IR	FR	N/A
Creation of variable Difference between Date of Surgery [dd.mm.yyyy] and Date of First Device Related Adverse Event [dd.mm.yyyy] in [days] (Variable(s): VISITDT; VISNAME; AEONSTDT)	Quantitative, ratio	Case summary with number and percentage of valid cases/values, missing cases/values (if any) and total cases/values. Mean, median, interquartile range, maximum, minimum, standard deviation, 95% confidence interval for mean, Shapiro-Wilk Test.		х	

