7.1. FREQUENCIES

All answered response options must be listed with the appropriate label, other response options do not have to be displayed necessarily. In the event of missing answers, the frequencies must be included in an extra row as well ("*Missing*"). All given answers must be added up in an extra row ("*Total*"). In addition to the number of frequencies, percentages must be displayed in a separate column.

"Analysis Section" – "Variable Label" – Frequencies					
Characteristic		n	%		
"Variable Label"	"Response A"	"xxx"	"xxx "		
	"Response B"	"xxx "	"xxx "		
	Missing	"xxx "	"xxx "		
	Total	"xxx"	"xxx "		

"Analysis Section" – "Variable Label" – Frequencies

Table 7.1.1: Frequencies Table Template

If multiple subgroups/clusters (e.g. Sites, Visits) should be displayed in one table, an extra column ("*Group X*") and/or extra rows ("*Group Y*") must be added. Same applies to (sub-) questions, which can be merged in one table. It is recommended to add an extra "Total" column and row, for adding up the subgroups, if possible, from a statistical point of view. In addition, subgroups must be named in the headline as well ("*by Group X and by Group Y*").

"Analysis Section" – "Variable Label" – Frequencies – by "Group X" and "Group Y"

Characteristic		"Group X1"		"Group X2"		Total	
		n	%	n	%	n	%
	"Response A"	"xxx "	"xxx"	"xxx "	"xxx"	"xxx"	"xxx"
"Crown VI"	"Response B"	"xxx "	"xxx"	"xxx"	"xxx "	"xxx"	"xxx"
Group II	Missing	"xxx "	"xxx"	"xxx"	"xxx "	"xxx"	"xxx"
Total	Total	"xxx "	"xxx"	"xxx"	"xxx "	"xxx"	"xxx"
	"Response A"	"xxx "	"xxx"	"xxx"	"xxx"	"xxx"	"xxx "
"Crown V2	"Response B"	"xxx "	"xxx"	"xxx"	"xxx"	"xxx"	"xxx"
Group 12	Missing	"xxx "	"xxx"	"xxx"	"xxx"	"xxx"	"xxx"
	Total	"xxx "	"xxx"	"xxx "	"xxx"	"xxx"	"xxx"
	"Total Response A"	"xxx "	"xxx"	"xxx "	"xxx"	"xxx"	"xxx"
Total	"Total Response B"	"xxx "	"xxx"	"xxx "	"xxx"	"xxx"	"xxx"
	Missing	"xxx "	"xxx"	"xxx"	"xxx"	"xxx"	"xxx"
	Total	"xxx"	"xxx"	"xxx"	"xxx"	"xxx"	"xxx"

Table 7.1.2: Grouped Frequencies Table Template

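### Bone consolidation by 12 months: the SAP has no rule for combining visits, and leaves the status of waived assessments and the percentage base undefined

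*SAP*

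**What the plan says.** The endpoint carries the same time frame in both documents. Protocol 8.2: "Bone consolidation will be assessed by 12 months as measured by Investigator assessment". SAP 3.1.2: "bone consolidation will be assessed by 12 months as measured by Investigator assessment". The protocol synopsis puts it as an objective: "demonstration of bone consolidation in correct alignment will be measured by Investigator assessment by 12 months".

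Footnote d to the schedule, in Protocol 10.5 and SAP 4.4 alike, reads: "Once bone consolidation is observed, assessment no longer needs to be conducted at the additional follow-up visits".

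The analysis is visit by visit. SAP 6.5 says "The analysis of the Postoperative data must be performed separately for each follow-up visit listed in table 4.4", and adds that new variables are to be made individually for each follow-up visit. Table 6.6.2, the endpoint table, has three rows for the consolidation item (`BONECONS`) at 3, 6 and 12 months, each with frequencies and a missing proportion; the last is "12 Months - 4. Has the bone consolidated (consider weight- bearing, pain and imaging". Its analysis column is headed as containing recodes, but none is given.

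On missing data, SAP 4.6 promises "the number and percentage of missing cases for each analyzed variable in relation to the enrolled cases for each post-operative assessment", and the template in SAP 7.1 adds: "In the event of missing answers, the frequencies must be included in an extra row as well". Neither says whether an assessment waived under footnote d is a missing case. The template asks for percentages without naming their base.

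**The concern.** Consolidation by 12 months is most naturally read as the share of subjects who have consolidated at any time up to 12 months. The tables instead give the share answering yes at each visit. The two agree only if every healed subject is answered again at each later visit, and footnote d says that this is not required.

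A subject healed at 3 or 6 months may therefore have no 12-month answer while the site follows the plan exactly. If the item is blank, that subject leaves the yes row of the 12-month table, while subjects still unhealed stay in. The table is then weighted towards slow healers, and its value can differ between sites according to how many healed subjects each one re-assesses.

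The SAP shows elsewhere that it can derive subject-level variables. It builds combined variables for first device-related event (Table 6.6.3), mortality (6.7.4) and revision (6.7.5), and cross-visit change variables for weight-bearing and external support (6.7.2, 6.7.3). Consolidation has none. The combining rule and denominator would then be chosen after the data are seen, in an unblinded single-arm study whose annual reports already include this item (Table 6.5.1).

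**Working it through.** The plan gives no consolidation rate, target or sample size for this endpoint, so there is no figure to reproduce. The calculation shows direction and a range.

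**Inputs.** From the SAP: 80 enrolled (2.2) and 20% drop-out (3.2). Assumed, with no source in the documents:
- p12, the true cumulative consolidation by 12 months
- p6, the same by 6 months
- r, the share of those healed by 6 months who are re-assessed at 12 months and again answered yes

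Everyone unhealed at 6 months is taken to be answered at 12 months.

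**Formula, answered base.**
- Yes = r·p6 + (p12 − p6)
- Answered = r·p6 + (1 − p6)
- 12-month figure = (r·p6 + p12 − p6) / (r·p6 + 1 − p6)

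The unhealed share 1 − p12 stays in the table while the denominator shrinks. The figure is therefore below p12 whenever r < 1, p6 > 0 and p12 < 1.

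**Results for p12 = 95%.**

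| r | p6 = 50% | p6 = 85% |
|---|---|---|
| 100% | 95% | 95% |
| 75% | 0.825/0.875 = 94.3% | 0.7375/0.7875 = 93.7% |
| 50% | 0.70/0.75 = 93.3% | 0.525/0.575 = 91.3% |
| 25% | 0.575/0.625 = 92.0% | 0.3125/0.3625 = 86.2% |
| 0 | 0.45/0.50 = 90.0% | 0.10/0.15 = 66.7% |

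With p12 = 90% and r = 50%, the figure is 0.65/0.75 = 86.7% (p6 = 50%) or 0.475/0.575 = 82.6% (p6 = 85%).

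**When it is negligible.** The gap is at most 1 point when r ≥ (D − 1 + p6)/p6, with D = (1 − p12)/((1 − p12) + 0.01).
- p12 = 95%: D = 0.05/0.06 = 0.8333, so r ≥ 0.667 (p6 = 50%) to 0.804 (p6 = 85%).
- p12 = 90%: D = 0.10/0.11 = 0.9091, so r ≥ 0.818 to 0.893.

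**Effect of the base, in counts.** Suppose 16 of 80 (20%) are lost before any observed consolidation, and 61 of the other 64 heal. The cumulative result is 61/64 = 95.3% of known status, or 61/80 = 76.3% of enrolled. With h healed by 6 months and k of them re-assessed at 12, answered = 64 − h + k and yes = 61 − h + k.

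| h, k | Answered base | Enrolled base | No answer |
|---|---|---|---|
| 32, 16 | 45/48 = 93.8% | 45/80 = 56.3% | 32/80 |
| 51, 25 | 35/38 = 92.1% | 35/80 = 43.8% | 42/80 |

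At about half re-assessed, the gap is 1.6 to 3.2 points on the answered base, and 20 to 32.5 points if percentages were taken over all enrolled. The SAP does not specify that second base, so those figures show only that the choice matters.

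**Adding the visits is no substitute.** In the first row, if nobody healed at 3 months was asked again at 6, the yes counts sum to 32 + 45 = 77. Only 61 subjects healed; the excess is the 16 asked twice. The SAP does not propose this sum.

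**The case against.** The strongest reply is that the shortfall may never arise. Footnote d permits skipping and does not require it. The item asks about a state, so a site could enter yes for a bone already known to have healed. Several passages make a completed 12-month form plausible:
- Protocol 7 and SAP 2.2 add a 12-month visit to standard of care.
- Footnote a, on standard-of-care scheduling, is attached to the 3- and 6-month visits only.
- Protocol 10.4 lists consolidation among the follow-up evaluations and asks for every effort to obtain data.
- Weight-bearing and external support, on the same form (Table 6.5.1), are planned at 12 months with no exemption after healing.

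Footnote g points the other way, since it moves the SF-36 of healed subjects to the phone. The EDC coding rules are not in the documents. So r is unknown and has not been shown to be low. This part of the objection stands.

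It is also fair that the endpoint is descriptive, that any missing row would be printed, that `BONECONS` is held by subject and visit so the cumulative figure can be rebuilt, and that Protocol 11.4 requires SAP deviations to be listed. These points lower the severity. They do not supply the rule.

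Finally, the phrase about 12 months could be read as the period in which assessments take place and not as a cumulative result. That ambiguity is itself a reason to define the endpoint.

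**Conclusion.** The gap is real and of low severity. Three things are undefined for the only efficacy secondary endpoint: how visits combine, how a waived assessment is classed, and the percentage base. Any shortfall in the 12-month table depends on healed subjects being skipped and the item left blank. On the assumed rates with p12 = 95%, the answered-base shortfall runs from nil at full re-assessment, through 1.7 to 3.7 points at one half (95 − 93.3; 95 − 91.3), to 5 to 28 points at none (95 − 90; 95 − 66.7).

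A reader might infer more, and the documents do not support it:
- *That the table will understate consolidation.* Re-assessment practice and EDC coding are not shown.
- *That the SAP counts waived assessments as missing.* SAP 4.6 and 7.1 speak of missing cases and missing answers; whether waived ones belong there is not stated.
- *That a gap of 20 points or more is to be expected.* That needs assumed healing and re-assessment rates together with an enrolled base that the SAP does not prescribe.

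The primary endpoint is not affected, and no hypothesis or target rests on this result.

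**What to change.** In SAP 6.6, add a derived variable, *Consolidated by visit X*, equal to yes if `BONECONS` was yes at visit X or at any earlier visit. Report the cumulative proportion by 3, 6 and 12 months, and name the 12-month value as the secondary endpoint. State its denominator before the data are analysed, including how subjects lost before any observed consolidation are counted.

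In Tables 6.5.1 and 6.6.2, show a blank that follows an earlier yes as *previously consolidated*, separate from *Missing*, and state the percentage base.

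Two additions are optional: a second denominator (known status alongside all enrolled), and a listing of any no recorded after an earlier yes.

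The cost is a few lines of SAP text and one variable derived from data already collected. Visits and the CRF do not change.
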